#### **6.4.5 Safety event follow-up**

Medical follow-up of any type of safety event will continue until the abnormality resolves, or an adequate medical explanation is apparent.

Documentation of all follow-up information regarding the AEs must be provided in the eCRF and, in accordance to the reporting requirements described above.

If the subject is withdrawn from study treatment due to an AE, the AE and the reason for withdrawal from the study is to be documented clearly in the eCRF.

## **7 General study management**

Study Start is not allowed before all of the necessary approval documents (IEC/IRB approval, signed CIP, signed CSA, regulatory approval if applicable) are available and the study site has been initiated by DENTSPLY Implants.

### **7.1 Changes to the Clinical Investigation Plan (CIP)**

Study procedures will not be changed without the mutual agreement of the coordinating Investigator and DENTSPLY Implants. If it is necessary for the CIP to be amended, the amendment and/or a new version of the CIP (Substantial Amendment) must be notified to or approved by each IEC/IRB, and if applicable, also the local Regulatory Authority, before implementation. Local requirements must be followed. If a CIP amendment requires a change to a particular study site's ICF, then DENTSPLY Implants and the study site's IEC/IRB must be notified. Approval of the revised ICF by DENTSPLY Implants and by the IEC/IRB is required before the revised form is used. DENTSPLY Implants will distribute amendments and new versions of the CIP to each Principal Investigator(s), who in turn is responsible for the distribution of these documents to his or her IEC/IRB, and to the staff at his or her study site. The distribution of these documents to the Regulatory Authority will be handled according to local practice.

In general, a Non-substantial Amendment does not require a notification to or approval by IEC/IRB.

### **7.2 Monitoring**

Before the first subject enters the study, a representative of DENTSPLY Implants will visit the investigational study site to:

- Determine the adequacy of the facilities
- Discuss with the Investigator(s) (and other personnel involved in the study) their responsibilities with regard to CIP adherence, and the responsibilities of DENTSPLY Implants or its representatives.

During the course of the study, a study monitor from DENTSPLY Implants or representative will have regular contacts with the study site, including visits to:

- Provide information and support to the Investigator(s)
- Confirm that facilities remain acceptable
- Confirm that the investigational team is adhering to the CIP, that data are being accurately recorded in the eCRFs, and that Investigational Product accountability checks are being performed
- Perform source data verification (SDV, a comparison of the data in the eCRFs with the subject's medical records at the hospital or practice, and other records relevant to the study). This will require direct access to all original records for each subject.

The study monitor or another DENTSPLY Implants representative will be available between visits if the Investigator(s) or other staff at the study site needs information and advice.

### **7.3 Audits and inspections**

Authorized representatives of DENTSPLY Implants, a Regulatory Authority, an IEC/IRB may visit the study site to perform audits or inspections, including source data verification. The purpose of a DENTSPLY Implants audit or inspection is to systematically and independently examine all study-related activities and documents to determine whether these activities were conducted, and data were recorded, analyzed, and accurately reported according to the CIP, ISO 14155 and any applicable regulatory requirements. The Investigator should contact DENTSPLY Implants immediately if contacted by a regulatory agency about an inspection at his or her site.

#### 7.4 Training of study site staff

The Principal Investigator must maintain a record of all individuals involved in the study (medical, nursing and other staff), i.e. a Responsibility and Signature Log. He or she shall ensure that appropriate training relevant to the study is given to all of these staff, and that any new information of relevance to the performance of this study is forwarded to the staff involved. DENTSPLY Implants will support the training.

Before the first subject is entered into the study, the study staff will be trained to use the EDC system (eCFR) by DENTSPLY Implants personnel or delegates.

#### 7.5 Deviations from the Clinical Investigational Plan

The Investigator is not allowed to deviate from the CIP except in emergency situations, with purpose to protect a subject's rights, safety and wellbeing.

In such cases, the Investigator may proceed without prior approval of DENTSPLY Implants and the EC. Furthermore, such deviations shall be documented and reported as soon as possible to DENTSPLY Implants and the IEC.

Should the Investigator break any obligations under the CIP or CSA (including a failure without just cause to meet a timeline) and fail to remedy such a breach where it is capable of cure, DENTSPLY Implants retains the right to disqualify the study site from further study participation.

All CIP deviations must be directly reported to the Study Team Leader, by either the Investigator or Monitor.

#### 7.6 Study agreements

The Principal Investigator at each study site should comply with all the terms, conditions, and obligations of the CSA for this study. In the event of any inconsistency between this CIP and the CSA, the terms of CIP shall prevail with respect to the conduct of the study and the treatment of subjects and in all other respects, not relating to study conduct or treatment of subjects, the terms of the CSA shall prevail.

Agreements between DENTSPLY Implants and the Principal Investigator should be in place before any study-related procedures can take place, or subjects are enrolled.

#### 7.7 Early termination of the study

The end of the study is defined as 'the last visit of the last subject undergoing the study'.

The study may be terminated at individual study sites if the study procedures are not being performed according to regulations (Declaration of Helsinki, ISO 14155 and applicable regulatory requirements) or if recruitment is slow. DENTSPLY Implants may also terminate the entire study prematurely if concerns for safety arise within this study or in any other study with the Investigational Product.

#### 7.8 Publication policy

The results from the SIMPLANT evaluation (no. of avoided augmentations) as well as the 1-, 3- and 5-year data are planned to be compiled into articles and submitted to peer-reviewed journals. The data will be provided by DENTSPYL Implants and the writing process will be coordinated by the International Co-ordinating Investigator.

### 8 Investigational Products

Product Name	ANKYLOS® C/X Implant A 6.6
Diameter	3.5 mm
Lengths	6.6 mm
Characteristics	Dental endosseous implant

Packaging	Sterile, double package
Other products	
Cover screws	ANKYLOS® C/X Cover Screw
Abutments	ANKYLOS® Balance Base Abutment C/ narrow – available in four heights, i.e. 0.75, 1.5, 3.0 and 4.5 mm. Both the straight (A0) and the 15° angled (A15) abutments are allowed in the study. NB! The 30° angled versions (A30) are not allowed in the study.
Suprastructure	Occlusally screw-retained ATLANTIS™ ISUS bridges (titanium)
Veneering	Subjects will, in consultation with the Investigator, be able to choose one out of four alternatives: 
 
• Resin
 
• Composite
 
• Composite and Ceramic
 
• Ceramic
 

### 8.1 Indications for use

ANKYLOS C/X 6.6 mm implants are intended for replacing missing teeth and for supporting single tooth restorations, bridges and prostheses (overdentures) to restore chewing function of the patient.

### 8.2 Labeling

The packing and labeling of the Investigational Product will be performed by DENTSPLY Implants in accordance with ISO 14155. The labels will be available in English language and in accordance with local regulations.

### 8.3 Storage and accountability records

All Investigational Products must be kept in a dry and secure (locked) area. Investigational Products will be used only for this study and only in accordance with the CIP.

The Principal Investigator is responsible for maintaining accurate records (Device Accountability Form) of the dispensing of Investigational Products. Any Investigational Products accidentally or deliberately destroyed must be accounted for and discrepancies between amounts dispensed and returned should be explained. All unused products must be returned to DENTSPLY Implants when treatment of the last subject has been completed.

## 9 Data collection and data management

### 9.1 Case Report Form recording and processing

Data will be entered into electronic Case Report Forms (eCRFs) using Viedoc™, a web based Electronic Data Capture (EDC) system used by DENTSPLY Implants, at the study site. Trained and authorized study site personnel will be responsible for entering data into Viedoc™. Data entered into Viedoc™ will be immediately saved to a central database, hosted by a 3rd party, PCG Solutions.

When data has been entered, reviewed, edited and source data has been verified, the data will be locked to prevent further editing and, if not already done, the Principal Investigator will be prompted to sign the eCRF electronically. A contemporaneous copy of the CRF must be available for the study site.

Data queries will be raised for inconsistent, impossible or missing data. The study site personnel are required to resolve any such queries. All entries to the study database will be available in an audit trail.

Results from central evaluations of CBCT-scans/SIMPLANT files and X-rays will be entered directly into Viedoc™ by DENTSPLY Implants personnel or the evaluators.

When data verification and validation is complete and data is deemed clean, clean file will be declared. Any treatment revealing data may thereafter be added and the database will be locked.

## **9.2 Storage of data**

Readable copies of the eCRF data, stored on a CD-ROM or a DVD will be archived in the ISF at the study site after Clean File. The ISF copy will be created either by 3rd party, PCG Solutions or by trained study site personnel. DENTSPLY Implants will not at any time point be in control of the ISF data archive, unless the copy is sealed by 3rd party and then only for the purpose of delivering it to the study site.

DENTSPLY Implants will assume responsibility for the long-term storage of all data in compliance with the applicable local laws and ISO 14155 [29].

Study data will be securely stored at DENTSPLY Implants, with restricted access. Data will be retained at DENTSPLY Implants for 25 years after study closure.

# **10 Statistical methods and data analysis**

## **10.1 Statistical evaluation – general aspects**

When using the terminology descriptive statistics it is meant that the number of subjects (N), mean, median, standard deviation (SD), minimum (min) and maximum (max) values will be presented for continuous data and frequencies and percentages for categorical data. If nothing else is stated, descriptive statistics will be given for each variable in the study.

When calculating p-values a non-parametric statistical approach will be applied because of the nature of the data. Confidence interval will be calculated using distribution assumptions.

No sub-groups are defined but it cannot be ruled out that such are defined during the conduct of the study or in the analysis of the study data. The statistical analysis will then follow the intentions presented in this section and the possibility of multiplicity will be considered.

### **10.1.1 Demographics and other baseline characteristics**

Demographics and other baseline characteristics will be presented by means of descriptive statistics.

### **10.1.2 Covariates and prognostic variables**

No covariates are judged to influence the outcome of the primary or any of the secondary variables.

### **10.1.3 Handling of dropouts and missing data**

Subjects dropping out from the study during the recruitment period will be replaced. Subjects dropping out after completion of the recruitment period will not be replaced but compensated for in the sample size estimation, see section 10.4.

### **10.1.4 Multi-center**

This study is a multi-center study. However, there is no a priori reason to suspect that there will be any qualitative differences between the study sites regarding any of the efficacy variables nor regarding

the safety variables. Therefore the primary statistical analysis will not include study sites in the model but the result of the primary variable will as well be presented by study site.

## 10.2 Description of analysis sets

The study will be analyzed using a Safety (S) and an Intention-to-Treat (ITT) population approach. The S analysis set will consist of all included subjects who have been treated with implants. ITT analysis set will consist of all subjects fulfilling the inclusion criteria, none of the exclusion criteria and have had their implants installed as planned. Treatment efficacy related conclusions will be based on the results from the ITT analysis.

All subject data will be included in subject data listings.

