### 5.5.3 Procedure for handling enrolled subjects that fail to fulfill inclusion/ exclusion criteria

If a subject has been enrolled, but no study-related surgical procedures were performed (withdrawal of consent, not meeting all pre-surgical criteria etc.) the Investigator must document this in the subject's medical records. In case of the subject's unavailability the Investigator will document this as well. Termination section in the eCRF should be completed. No follow-up is necessary.

If a subject has been enrolled and study-related surgery started, but for any reason no Investigational Product could be inserted the Investigator must document this in the subject's medical records. Termination section in the eCRF should be completed. No follow-up is necessary.

If a subject has been enrolled and study-related surgery has been completed, although the inclusion/exclusion criteria are violated, it will be decided on a case-by-case basis by DENTSPLY Implants if the subject will continue in the study. If so, the subject will not be part of the Intention-to-Treat (ITT) analysis and the reimbursement of the treatment will be reduced as described in the CSA.

If a subject lose a study implant and a new implant is inserted, the new implant should not be registered in the eCRF. If a subject loses all study implants, the subject will discontinue the study.

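### Subjects whose study surgery is abandoned without an implant fall outside the Safety set, their follow-up rule conflicts with two other sections, and follow-up of implanted eligibility violators rests on undefined sponsor discretion

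*Combined protocol and SAP*

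**What the plan says.** Section 10.2 defines two analysis sets. For safety: "The S analysis set will consist of all included subjects who have been treated with implants". The ITT set is narrower and requires eligibility and implants installed as planned. The same section adds: "All subject data will be included in subject data listings". Section 10.3 makes the safety analysis purely descriptive.

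Section 5.5.3 describes a group that has had surgery but has no device: "If a subject has been enrolled and study-related surgery started, but for any reason no Investigational Product could be inserted". For this group the instruction ends: "Termination section in the eCRF should be completed. No follow-up is necessary".

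For subjects implanted despite an eligibility violation, Section 5.5.3 says that "it will be decided on a case-by-case basis by DENTSPLY Implants if the subject will continue in the study". If they continue, "the subject will not be part of the Intention-to-Treat (ITT) analysis". Nothing is said there about the Safety set.

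Section 6.4.5 is general: "Medical follow-up of any type of safety event will continue until the abnormality resolves, or an adequate medical explanation is apparent". Section 5.5.2 likewise calls for adverse events to be followed up in subjects who discontinue. Section 6.4.2 counts adverse events whether or not the subject was exposed to the device, and classes an event judged related to the device or the procedure as an ADE. Appendix B has adverse events documented from Visit 2, so the surgical visit is covered.

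**The concern.** The rule for recording safety events and the rule for summarising them cover different people. Events are recorded from before surgery and regardless of exposure, but the Safety set begins only once an implant has been placed. An event caused by an operation that ended without an implant is an ADE by Section 6.4.2, yet it has no place in a Safety-set table. Because descriptive tables are the whole safety analysis, a listing keeps the record but gives no numerator or denominator.

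The plan foresees that some operations may not go as intended. Section 5.1.1 says eligibility cannot be confirmed until after the CBCT and/or implant placement, Section 5.3.3.1 requires the bone criteria to be met at Visit 3, and Section 5.5.3 gives abandoned surgery its own paragraph.

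The follow-up waiver for the same group makes no exception for an event that is still open. A site reading Section 5.5.3 alone could close such a subject while Sections 5.5.2 and 6.4.5 say otherwise.

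For implanted violators the issue is different. They carry study implants, and some exclusion criteria (items 9 and 10) describe conditions or medication that the plan itself regards as compromising healing or osseointegration. If the sponsor ends their participation, scheduled collection of later implant losses stops, and Section 6.4.1.5 classes implant loss as an ADE. Without stated criteria, that decision could be made with knowledge of how the subject is faring.

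**Working it through.** **Step 1. Who is where.** Reading Sections 5.5.2, 5.5.3, 6.4.2, 6.4.5 and 10.2 together:

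| Group | Safety set (10.2) | ITT (5.5.3, 10.2) | Listings (10.2) | Follow-up |
|---|---|---|---|---|
| Surgery started, no implant placed | Out | Out | In | Waived in 5.5.3; open events followed under 5.5.2 and 6.4.5 |
| Implanted, eligibility violated, allowed to continue | In, by the wording of 10.2 | Out | In | Scheduled visits |
| Implanted, eligibility violated, participation ended | In, events up to exit | Out | In | Open events only; no scheduled collection of later losses |

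That safety summaries use the Safety set is an inference from Section 10.2, which reserves efficacy conclusions for ITT; Section 10.3 does not name the set. One word also needs defining. Section 10.2 speaks of included subjects, while Section 5.3.1 sets included subjects against those who fail the selection criteria, so a strict reader might question whether an implanted violator is included.

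**Step 2. The plan's figure.** No stated figure measures this issue. The only relevant number is 56, from Section 10.4: 304/6 = 50.7, rounded up to 51 evaluable subjects. Allowing 10% drop-out gives 51/0.90 = 56.7, against the plan's 56. The 56 counts subjects who receive implants, so abandoned operations are not in it, and widening the Safety set does not change the sample size.

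**Step 3. Effect on a subject-level ADE proportion.** Let x of the 56 implanted subjects have an ADE, let k further subjects have surgery started without an implant, and let j of those k have a procedure-related event. Then

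- under 10.2 as written: x/56
- from the start of surgery: (x + j)/(56 + k)

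The proportion rises only if j/k exceeds x/56. The documents give none of x, j or k, so all values below are assumptions. For x = 17, I take 5% loss (one minus the 95% survival used for sample size) of 56 × 6 = 336 implants, which is 16.8, and place each loss in a different subject.

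| x | x/56 | k | All k have an event | None of k has an event |
|---|---|---|---|---|
| 0 | 0% | 1 | 1/57 = 1.8% | 0/57 = 0% |
| 0 | 0% | 3 | 3/59 = 5.1% | 0/59 = 0% |
| 0 | 0% | 5 | 5/61 = 8.2% | 0/61 = 0% |
| 6 | 10.7% | 1 | 7/57 = 12.3% | 6/57 = 10.5% |
| 6 | 10.7% | 3 | 9/59 = 15.3% | 6/59 = 10.2% |
| 6 | 10.7% | 5 | 11/61 = 18.0% | 6/61 = 9.8% |
| 17 | 30.4% | 1 | 18/57 = 31.6% | 17/57 = 29.8% |
| 17 | 30.4% | 3 | 20/59 = 33.9% | 17/59 = 28.8% |

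With k = 3 the change runs from +5.1 points (x = 0, all with events) to −1.6 points (x = 17, none with events: 28.8 − 30.4).

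**Step 4. Violators.** Each implanted violator whose participation ends can lose up to five years of scheduled observation on six implants. Because violators are outside ITT, this does not alter the primary survival estimate; it affects the safety account.

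**The case against.** Five points can be made for the plan, and most have some force.

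First, a safety set built on subjects who received the device is a defensible way to describe implant safety. That stands, which is why a supplementary row or table would serve as well as a new definition.

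Second, the waiver follows directly on completing the termination form and may be meant to waive only scheduled visits, leaving Sections 5.5.2 and 6.4.5 in force. That is a plausible reading. A reader might infer that injured subjects are left without follow-up; the documents do not support that, because the general safety duties contain no exception for this group. But the waiver is unqualified and is the specific rule for these subjects, so the conflict of wording remains.

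Third, the group is probably small. It requires that no implant was placed at any of six sites, after CBCT planning, and Section 5.1.3 provides for a sinus procedure during surgery as an alternative to exclusion. A single complication at one site would not by itself put a subject in this group.

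Fourth, it is tempting to say that the safety tables omit implanted violators as well. They do not: Section 5.5.3 removes them from ITT only, and they have been treated with implants.

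Fifth, one might contrast Section 5.2 as keeping non-compliant subjects in for safety. It says only that they may continue, which is equally discretionary, so it adds nothing here.

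**Conclusion.** The point holds in a limited form. Subjects with abandoned surgery are outside every Safety-set summary although their procedure-related events are ADEs, and Section 5.5.3 conflicts in wording with Sections 5.5.2 and 6.4.5 on their follow-up. Implanted violators are in the Safety set up to exit, but how long they are observed depends on a decision with no stated criteria.

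The size and direction of the effect on ADE rates cannot be determined, since there are no counts for either group. A reader might infer that ADE rates are biased downward. That follows only if events are more frequent in abandoned operations than among the implanted; the table shows the rate can also fall. Nor is an increase of 1.8 to 5.1 points for one to three abandoned operations a general result: it needs an event in every added subject and none among the 56, which is unlikely when Section 6.4.2 lists implant loss and loose abutments or bridge screws as ADEs. Calling the affected subjects those most likely to be harmed also goes beyond the documents, which give no event rates by group.

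This is worth correcting before analysis because the correction is cheap, but it does not touch the primary test or the sample size.

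**What to change.** 1. In Section 10.2, define the Safety set as all subjects in whom study surgery was started. Alternatively, keep the present definition and add a separate row or table giving the number of abandoned operations and their adverse events. Either way, name the set used for the safety summaries.
2. In the same section, define what included means and state that subjects implanted despite an eligibility violation belong to the Safety set.
3. Reconcile the follow-up waiver in Section 5.5.3 with Sections 5.5.2 and 6.4.5, so that a site finds one rule for a subject with an open event after abandoned surgery. Which rule should govern is for the sponsor and investigators to settle.
4. Reconcile the case-by-case decision in Section 5.5.3 with the discontinuation grounds in Section 5.5.1, whose list is open but does not name eligibility violation. Pre-specify, independently of outcome, how safety and implant-loss data are collected for implanted violators. A blanket rule that every implanted subject stays in follow-up unless consent is withdrawn would go too far, because it would override the other grounds in Section 5.5.1.

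The cost is a wording change and slightly more reporting work, with possibly some extra data collection for violators. Safety figures may look slightly less favourable. The 56 planned subjects are unaffected.

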**5.2 Compliance**

Subjects will be asked to return to all visits and to follow the Investigator's instructions regarding the treatment at any time (post-surgery activities etc.). Non-compliance is defined as subjects obviously disregarding the Investigator's instructions. Subjects judged to be non-compliant may continue in the study for safety reasons, but the reimbursement of the treatment will be reduced as described in the CSA.

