##### 6.3.1.1 Assessment of primary outcome variable

Implant survival will be evaluated clinically and radiographically by counting the number of implants remaining *in situ*. Any implant that has been removed or lost after implant placement (Visit 3) will be considered a failure, whatever the reason for removal/loss.

Implant survival rate will be analyzed on an implant level (i.e. percent of survived implants) as well as subject level (i.e. percentage of subjects with no lost implants).

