#### **6.4.1.5 Device Deficiency**

Inadequacy of a medical device with respect to its identity, quality, durability, reliability, safety or performance. This includes malfunctions, use errors, and inadequate labeling.

**NB!** Pay special attention to device deficiencies that might have led to an SADE if:

- a) suitable action had not been taken or
- b) intervention had not been made or
- c) circumstances had been less fortunate.

**DENTSPLY Implants clarification:** A device deficiency is an event associated with the product itself, not with the subject. The loss of an implant is not defined as a device deficiency; it is defined as an ADE.

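### The set called ITT holds only eligible subjects implanted as planned, efficacy conclusions rest on it, and no survival test in all treated subjects is specified

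*Combined protocol and SAP*

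**What the plan says.** Section 10.2 defines two analysis sets. For the first: "The S analysis set will consist of all included subjects who have been treated with implants". For the second: "ITT analysis set will consist of all subjects fulfilling the inclusion criteria, none of the exclusion criteria and have had their implants installed as planned". It then adds: "Treatment efficacy related conclusions will be based on the results from the ITT analysis".

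Section 5.5.3 covers subjects whose surgery was completed although a criterion was violated. For them, "it will be decided on a case-by-case basis by DENTSPLY Implants if the subject will continue in the study", and if they do continue, "the subject will not be part of the Intention-to-Treat (ITT) analysis".

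The primary outcome is defined broadly in section 6.3.1.1: "Any implant that has been removed or lost after implant placement (Visit 3) will be considered a failure, whatever the reason for removal/loss".

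Section 10.3 specifies one test of survival, the exact binomial test with a confidence interval, and names no analysis set for it. Safety is to be described only. Section 10.4 gives the hypothesis: survival below 90%, tested at a one-sided 0.025.

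**The concern.** An intention-to-treat set in a single-arm device study would normally hold every subject who received the device. This one removes treated subjects on two grounds: eligibility, and how placement went. An outcome that counts loss for any reason is thus judged in a set chosen partly by how the surgery turned out. With a fixed 90% goal and no comparator, nothing offsets such a selection.

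Three gaps add to this:

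- **Definition.** 'Installed as planned' could mean six implants at the positions chosen at Visit 2, or any placement that section 5.1.3 allows. That section keeps subjects with an intra-operative sinus floor elevation in the study, while section 5.3.3.1 requires the 7 mm bone height to be met at Visit 3. Their place in the set is not stated.
- **Timing.** No date fixes membership. The study is open, and exclusions 9 and 10 call for judgement about what would compromise healing or osseointegration. A violation could be recognised after losses are known.
- **Follow-up.** Because the sponsor decides case by case whether a treated violator continues, later survival status may not be collected and could not be recovered for an all-treated analysis.

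Exclusions 9 and 10 concern conditions and medication that threaten osseointegration. Worse survival among violators is therefore plausible on the plan's own logic, though the documents do not show it.

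**Working it through.** **Inputs from the plan (section 10.4).** Null rate 0.90, one-sided 0.025, exact binomial test, 6 implants per subject treated as independent, 304 implants for 90% power at a true rate of 0.95, 56 subjects to be treated.

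**The plan's own figure.** The rule is to find the largest number of failures f with P(X ≤ f | n, 0.10) ≤ 0.025. At n = 304, f = 20; the attained level is 0.0243 and power at 95% survival is 0.914, which meets the 90% target. Then 304/6 = 50.7, so 51 subjects. The sample size is not in question.

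**Assumptions not in the plan.** The number of subjects removed (k) and their implant survival (s). The target is survival in all 56 treated subjects, set at exactly 90%, with complete data.

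**Step 1: survival in the retained set.** Retained rate = (0.90 × 56 − k × s)/(56 − k). For example, k = 5 and s = 0.80 give (50.4 − 4.0)/51 = 0.9098; k = 2 and s = 0.85 give (50.4 − 1.7)/54 = 0.9019.

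**Step 2: chance that the retained set meets the goal.** This is P(X ≤ f | n, 1 − retained rate), with n = 6 × (56 − k).

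| Removed | Implants | Max. failures | s = 80% | s = 85% | s = 90% (like the rest) |
|---|---|---|---|---|---|
| 0 | 336 | 22 | – | – | 1.75% |
| 1 | 330 | 22 | 2.9% | 2.5% | 2.2% |
| 2 | 324 | 21 | 2.9% | 2.25% | 1.7% |
| 3 | 318 | 21 | 4.6% | 3.2% | 2.2% |
| 4 | 312 | 20 | 4.7% | 2.9% | 1.7% |
| 5 | 306 | 20 | 7.4% | 4.2% | 2.2% |

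The last column is the test's own attained level at each n. It moves between 1.7% and 2.2% with no bias at all, so part of the movement in the other columns is the saw-tooth of an exact test.

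**Step 3: can the conclusion change?** Take an example at the cut-off. With 3 subjects removed, 21 failures in 318 implants pass (p = 0.0224). If their 18 implants carry 2 failures, the all-treated count is 23 in 336 (p = 0.0284), which misses. If they carry 1, it is 22 in 336 (p = 0.0175), which passes. The number expected at the retained rate is 18 × 21/318 = 1.2. A reversal is possible, but only close to the boundary.

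**Step 4: the same test on all treated subjects.** At 336 implants with complete data, up to 22 failures pass, and power at 95% survival is 0.919.

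**The case against.** The strongest reply is that a claim limited to eligible, properly implanted patients is a legitimate choice of population. In the illustration the retained set truly survives above 90%, so rejecting the null is correct for that set; it is wrong only if all treated subjects are the target. This stands, and the percentages above depend on that target. It does not rescue the ITT label, and it is weaker for 'installed as planned', which depends on the surgery itself.

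The number removed may also be small. Eligibility is checked at Visits 1 to 3, subjects who fail before surgery leave the study, deviations are restricted (section 7.5) and sites are monitored (section 7.2). This stands too. Figures above 5% need five subjects removed at 80% survival.

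Four stronger readings are tempting, and the documents do not support them:

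- *A reader might infer that the losses of removed subjects are hidden.* They are not: "The loss of an implant is not defined as a device deficiency; it is defined as an ADE". All subject data are listed (section 10.2), and section 10.1 probably brings survival into descriptive Safety-set statistics. What is missing is a specified test.
- *A reader might infer that the plan expressly confines the survival test to this set.* Section 10.3 attaches no set to the test; its use of the ITT set is inferred from the sentence in 10.2 on efficacy conclusions.
- *A reader might infer that this is a full per-protocol set.* Section 10.2 sets no condition on later compliance, and section 5.2 says: "Subjects judged to be non-compliant may continue in the study for safety reasons".
- *A reader might infer that the exclusions leave the study underpowered.* Removing 1 to 5 of 56 subjects with complete data leaves power at 0.895 to 0.930. Larger losses appear only if unreplaced removals are added to the full 10% drop-out, which the documents do not say will happen.

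**Conclusion.** The concern holds as a fault of definition and specification. The set that carries the efficacy conclusions is mislabelled, one of its conditions is undefined, its membership has no fixing date, and no all-treated survival test is specified. This should be fixed.

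The size of any bias cannot be derived from the documents. Its direction is conditional: upward for all treated subjects if those removed survive worse, none if they resemble the rest. The illustrative range of 1.7% to 7.4% for 2 to 5 removals rests on an assumed number removed, their assumed survival, all treated subjects as the target, complete data, and the plan's assumption that implants are independent. It shows what could happen; it is not an estimate for this trial.

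**What to change.** - **Primary set (sections 10.2, 10.3 and 5.5.3).** Name all subjects with at least one study implant placed, regardless of eligibility violations, as the set for the exact binomial test. Say so explicitly rather than pointing to the Safety set: its definition speaks of included subjects, and section 5.3.1 contrasts being included with failing the selection criteria, so a literal reading could omit violators there as well.
- **Present set.** Rename it, for example 'eligible and implanted as planned', and use it for a sensitivity analysis. Define 'as planned' from facts known at the end of surgery. Record membership before survival outcomes are reviewed, at the latest before the 1-year partial clean file in section 10.5.
- **Follow-up (section 5.5.3).** Continue scheduled survival follow-up of treated violators who consent.
- **Reconciliation.** Reconcile section 5.1.3 on intra-operative sinus floor elevation with the bone-height criterion at Visit 3, so that these subjects' place in the renamed set is clear.

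The cost is wording in three sections, some continued follow-up, and possibly a slightly lower reported survival rate. The test and the planned 56 subjects do not change.
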